5.1 Screening and pre-randomisation evaluations

Written informed consent will be obtained before the subject undergoes any screening procedures as described in section 9.9.

All patients will have blood samples taken which will be processed and stored for later measurement of qHBsAg, ELISPOT assays and NK cell function.

Patients who consent to liver biopsy (estimated to be around 20 in number) will have a liver biopsy between screening and baseline with histological measurement of fibrosis, necroinflammatory scores and number of infected cells using immunohistochemistry for HBcAg and HBsAg. Biopsy tissue will be used to measure the level of cccDNA and to extract lymphoid cells for immunological phenotyping.

A Fibroscan (or ARFI) measurement will be made at baseline to confirm that cirrhosis is not present.

An ultrasound of the liver will be performed at baseline to exclude the presence of hepatocellular carcinoma.

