5.2 Randomisation

Patients will be electronically randomised using the InForm eCRF online custom built database to the two management arms in equal proportions using variable block sizes. Randomisation will be stratified by gender and by HBsAg titre at baseline (< or \ge 2000 IU/mI) as this is the strongest predictor of clinical outcome in interferon based treatment and was found to be a predictor of outcome in the Hadziyannis study.

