5.6 Laboratory Evaluations

(i) Haematology

Full blood counts and prothrombin times will be measured using standard methods in the routine haematology department at each participating site.

(ii) Biochemistry

Liver function tests (bilirubin, albumin, ALT, alkaline phosphatase), thyroid function tests (TSH & T4), glucose, electrolytes and creatinine will be measured using standard methods in the routine haematology department at each participating site.

(iii) HBV DNA

HBV DNA will be measured quantitatively using real-time PCR based assays in the routine virology departments at each participating site. Results will be reported back on the eCRF.

(iv) HBV genotype

Plasma from an EDTA specimen taken at week 4 will be collected and processed at each participating site and stored at -80°C until transported to Virology at UCLH. Genotyping will be performed by sequence analysis of the HBV DNA.

(v) HBsAg quantification

A quantitative HBsAg measure will be performed at each local hospital on a screening visit blood sample. The result will be used for stratification in the randomisation system.

HBsAg concentrations will be performed using the Abbott Architect qHBsAg system in [name] laboratory. Serum samples will be collected in the virology department at each participating site and stored at -80°C until transported, frozen, in batches to Virology at UCLH.

(vi) Liver Biopsy

In patients who consent to have a liver biopsy as part of the study the procedure will be performed by a trained hepatologist or radiologist and two passes will be made with the biopsy needle to obtain 2 liver specimens of 1.5 - 2 cm in length. One of these will be placed in to 10% formaldehyde and sent to the histology laboratory for paraffin embedding and sectioning. The first 2 sections will be used for standard H&E and pico-sirius red staining to assess necroinflammatory and fibrosis scores. Two sections will be used for immunohistochemistry staining for HBsAg and HBV core antigens. Two sections will be sent to [name] laboratory for measurement of cccDNA.

The second liver specimen will be collected in sterile PBS and sent by courier to [name] laboratory.

(vii) ELISPOT

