8.2 Data Analysis

(i) Primary Endpoint Analysis

This analysis will be performed primarily on an intention to treat (ITT) basis. The ITT population will be all subjects who have been randomized. Secondarily, a per protocol analysis will be performed. The per protocol population will be those confirmed to be eligible who have not resumed nucleos(t)ide analogues for patient/ physician preference and those, in the interferon arm, who have completed at least 8 weeks of interferon therapy. Rates of HBsAg loss will be compared between the two groups using logistic regression adjusting for the stratification factors HBsAg titre and centre. Results will be presented as odds ratios and their 95% confidence intervals.

(ii) Secondary outcomes

Secondary outcomes to be compared between the two groups will include the primary outcome assessed at one year and at two years from baseline. Kaplan-Meier plots will be produced to show the persistence of HBsAg. The plots will be supported by formal secondary analyses using Cox proportional hazards model methods

Achievement of the inactive carrier state (defined above) will be analysed using the same procedures as the primary outcome. A statistical analysis plan will be developed and approved by the Trial Steering committee prior to any regular analysis for reports to the Data Monitoring Committee. This plan will include details of the statistical methods to be used to analyse the outcomes, and describe the methods to undertake sensitivity analyses for handling missing data. The plan will contain conform with the Clinical Trials Unit standard operating procedures

(iii) Predictors of HBsAg Loss

Predictive factors for HBsAg loss will be explored using univariate and multivariate logistic regression analysis. Separate models will be fitted for the following variables: gender, age, duration of antiviral therapy, viral genotype, viral load pre-treatment, HBsAg titre, centre, peak ALT value post withdrawal, peak viral load post withdrawal, hepatic cccDNA, number of infected hepatocytes and ELISPOT counts. Odds ratios and their 95% confidence intervals produced from each of the models will be presented. Following this, a multivariate logistic regression analysis will be performed will include the variables that were statistically significant in the univariate analysis plus a variable for treatment group.

(iv) Safety analysis

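### The primary model most naturally enters HBsAg titre as a two-level stratum; a continuous log10 titre that every randomised patient already has would give a small gain in efficiency

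*Protocol*

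**What the plan says.** Section 8.2(i) of the Protocol compares the arms on HBsAg loss at three years: "Rates of HBsAg loss will be compared between the two groups using logistic regression adjusting for the stratification factors HBsAg titre and centre". Results are reported as odds ratios. Section 8.2(ii) analyses the inactive carrier state by the same procedures.

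Section 5.2 defines the titre stratum: "Randomisation will be stratified by gender and by HBsAg titre at baseline", with two levels, below 2000 IU/ml or at and above it. It justifies the choice on the ground that "this is the strongest predictor of clinical outcome in interferon based treatment", and adds that titre also predicted outcome in the cited withdrawal study.

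Section 5.6(v) states where the stratum comes from: "A quantitative HBsAg measure will be performed at each local hospital on a screening visit blood sample", followed by "The result will be used for stratification in the randomisation system". The same subsection describes a second, central measurement on a single platform: "HBsAg concentrations will be performed using the Abbott Architect qHBsAg system". Section 5.1 provides the material for later assay: "All patients will have blood samples taken which will be processed and stored for later measurement of qHBsAg, ELISPOT assays and NK cell function". Section 2.4 lists the reduction in quantitative HBsAg at 1, 6, 12, 24 and 36 months as a secondary endpoint, and that needs a pre-treatment value.

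**The concern.** Calling titre a stratification factor points to the split at 2000 IU/ml, since no other titre stratum is defined. A model with that factor treats a patient at 20 IU/ml like one at 1,900 IU/ml. Section 5.2 itself says that titre matters for outcome in interferon-based treatment and after withdrawal, which are the settings of the two arms.

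In a logistic model, prognostic information that is left out costs some power, and chance differences in titre between the arms within a stratum go unadjusted. The inactive-carrier analysis inherits the choice. The coding also affects the reported result, because odds ratios are non-collapsible: adjusting for the stratum and adjusting for continuous titre target different conditional odds ratios. That is a reason to settle the coding in advance.

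There is also a wording conflict. Section 5.2 describes the stratifying titre as a baseline value. Section 5.6(v) takes it from the screening sample, and the 5.3 schedules place screening 4 to 12 weeks before baseline.

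**Working it through.** **Inputs from the Protocol.** Rates of 20% and 40%, 90% power, P < 0.05, 109 per arm (8.1); 1:1 allocation and a titre cut at 2000 IU/ml (5.2). Two-sided testing is assumed. The Protocol gives neither the distribution of titre nor its odds ratio for HBsAg loss, so both are assumed and varied.

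**Step 1: the plan's own figure.** With pooled variance and no continuity correction,

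n = [1.960 × √(2 × 0.3 × 0.7) + 1.2816 × √(0.4 × 0.6 + 0.2 × 0.8)]² / 0.2² = (1.2702 + 0.8105)² / 0.04 = 108.2, rounded up to 109.

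The 109 per arm reproduces, with power of 90.2%.

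**Step 2: information kept by the split.** If log titre is normal and a share q of patients lies below the cut c (in SD units), the two-level version keeps φ(c)² / [q(1 − q)] of its variance.

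| Share below 2000 IU/ml | Kept | Lost |
|---|---|---|
| 50% | 0.3989² / 0.25 = 64% | 36% |
| 30% | 0.3477² / 0.21 = 58% | 42% |
| 20% | 0.2800² / 0.16 = 49% | 51% |
| 10% | 0.1755² / 0.09 = 34% | 66% |

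The formula is symmetric, so 70% below gives the same result as 30%.

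**Step 3: effect on power.** Logistic-regression simulation: 109 per arm, marginal rates of 20% and 40%, allocation balanced within the titre stratum, 2,000 trials per setting, Wald test of treatment. The models were fitted to the same simulated trials. Cells show power (%) with the two-level factor, then with continuous titre, then the gain in points.

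| Odds ratio per SD of log titre | 50% below cut | 30% below cut | 15% below cut |
|---|---|---|---|
| 1.5 | 91.30, 91.60 (+0.30) | 90.65, 90.80 (+0.15) | 91.15, 91.55 (+0.40) |
| 2 | 90.65, 91.80 (+1.15) | 92.65, 93.05 (+0.40) | 92.60, 93.50 (+0.90) |
| 3 | 93.20, 94.20 (+1.00) | 93.75, 94.55 (+0.80) | 92.55, 95.05 (+2.50) |
| 4 | 95.35, 96.55 (+1.20) | 94.65, 95.85 (+1.20) | 93.20, 95.95 (+2.75) |

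The Monte Carlo standard error of a single power is about √(0.92 × 0.08 / 2000) = 0.6 points, so small differences between cells should not be read closely.

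**Step 4: the same question on the log10 scale.** Assumed SD 0.7; odds ratios of 0.5, 0.3 and 0.2 per log10, equivalent to 1.6, 2.3 and 3.1 per SD (for example (1/0.5)^0.7 = 1.6); 4,000 trials per setting.

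| Mean log10 titre | Two-level | Continuous | Gain |
|---|---|---|---|
| 3.0 | 90.4 / 91.0 / 92.7% | 91.3 / 92.5 / 94.3% | 0.9 / 1.5 / 1.6 |
| 3.3 | 91.4 / 93.1 / 93.1% | 91.9 / 93.7 / 94.9% | 0.5 / 0.6 / 1.8 |

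The cut is at log10(2000) = 3.30. Under these two distributions the split keeps about 60% and 64% of the variance.

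**Limits.** Both simulations assume that log titre acts linearly and equally in both arms, and they leave out centre and gender. Linearity favours the continuous model.

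**The case against.** The strongest reply is that 8.2(i) never states the coding. Section 8.2(ii) leaves the details of the methods to a statistical analysis plan, which is not shown and may specify a continuous covariate. That stands: the two-level reading is an inference, though the natural one, because a plan that follows the sentence would enter the stratum.

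It is also true that adjusting for the stratum as randomised is conventional and valid. In every simulated setting the two-level model already exceeds the planned 90%, and the gain depends on assumed inputs. This limits the point to an improvement that costs little. It does not remove it, because the better covariate needs no new measurement.

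A third reply is that a central week-0 assay is not explicitly scheduled. The 5.3 tables mark qHBsAg at screening only; week 0 shows an HBsAg test not labelled quantitative, plus stored serum. The endpoint in 2.4 and the stored blood in 5.1 imply that a central baseline value can be obtained, but this is less certain than the local screening value. The fix therefore must not depend on it.

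Finally, the baseline and screening wording is minor: 5.6(v) makes clear which sample supplies the stratum, so randomisation itself can be carried out.

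**Conclusion.** The point holds as a small efficiency gain. Read with 5.2, the primary model most naturally uses the two-level stratum, which loses roughly a third to a half of the information in titre when 20% to 50% of patients lie on one side of the cut. Replacing it with continuous log10 titre adds about 0 to 3 points of power under the assumed distributions and odds ratios.

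A reader might infer more, and the documents do not support it:

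- **That most of the information is discarded.** This needs about 20% or fewer of the patients on one side of 2000 IU/ml, and the Protocol gives no distribution.
- **That the planned test is biased or underpowered.** It is valid, 109 per arm reproduces, and the stated power is kept.
- **That titre is the leading predictor in both arms.** Section 5.2 says so only for interferon-based treatment; after withdrawal it is simply a predictor.

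Which factors 8.2(i) lists is a separate question and plays no part in this conclusion.

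**What to change.** In 8.2(i), state that the primary model adjusts for log10 quantitative HBsAg measured before randomisation, as a continuous covariate alongside the randomisation strata. Name the source in advance: the local screening value that every randomised patient has, or the central assay on stored baseline serum where measured. Add a simple check of linearity on the log scale. State that the reported odds ratio is conditional on this covariate.

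In 5.2, describe the stratifying titre as measured at screening instead of baseline, to match 5.6(v).

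The cost is one sentence in 8.2(i), its counterpart in the analysis plan, and a wording change in 5.2. No new sample or visit is needed. The one practical check is that the database keeps the numerical screening result and not only its category. The downside is reliance on log-linearity.

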3.2 Design

The main trial for NUC-B will be performed in at least 10 sites in England. It is a randomised, open-label, multicentre trial comparing nucleoside / nucleotide analogue withdrawal against nucleoside/ nucleotide analogue withdrawal followed by a 16 week course of pegylated interferon in HBeAg-negative chronic hepatitis B virus infected patients. Patients will be followed for 3 years after randomisation.

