8 STATISTICAL ANALYSES

8.1 Sample Size and power considerations

HBsAg loss is the primary endpoint; the trial will compare the rate of HBsAg loss in patients three years after cessation of nucleos(t)ide analogues with the rate of HBsAg loss in patients treated with pegylated interferon after cessation of nucleos(t)ide analogues. Only one published study provides an estimate of the rate of HBsAg loss in patients who stopped treatment after 4 years of nucleos(t)ide analogues which was 10% at 1 year,18% at 2 years and 24% at 3 years. A similar study reported by Berg (EASL 2015) confirmed the 10% HBsAg loss reported at 1 year. In the present study we will recruit some patients who have had treatment with nucleos(t)ide analogues for only 3 years and we will therefore use a conservative assumption for the rate of HBsAg loss in this group at 15% at 2 years and 20% at 3 years.

There is no data on the rate of HBsAg loss in patients who have been treated with nucleos(t)ide analogues and subsequently been treated with pegylated interferon. In a trial of pegylated interferon for naïve HBeAg negative hepatitis infection 42.4% had lost HBsAg at the end of follow up if the level of HBV DNA had been <70 IU/ml at the end of treatment. As this is an exploratory study we have assumed that the rate of HBsAg loss in this group will be 30% at 2 years and 40% at 3 years. This increment would represent the very significant clinical benefit which would justify the use of interferon (with associated side effects) in this group of patients.

A trial with 90% power to detect a difference in HBsAg loss between these groups (40% vs 20%) at the P < 0.05 threshold would require 109 subjects in each arm. Therefore allowing for ~10% withdrawal / dropout in each arm we will aim to recruit 120 subjects to each arm; a total of 240 patients in total. If either arm is discontinued after the pilot, then there will still be at least 80% power in comparison with an alternative trial arm in the post pilot participants.

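### Kaplan-Meier plots of HBsAg persistence do not suit an outcome seen only at visits: with actual visit dates, the end of the curve overstates loss

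*Protocol*

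**What the plan says.** Protocol section 8.2(ii) lists the secondary analyses and states that "Kaplan-Meier plots will be produced to show the persistence of HBsAg". It then adds: "The plots will be supported by formal secondary analyses using Cox proportional hazards model methods". It does not say whether time runs to the actual or the scheduled visit date, or where the curve is cut. For further detail it points to a statistical analysis plan: "This plan will include details of the statistical methods to be used to analyse the outcomes".

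Three other places determine how such a curve behaves.

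- **Testing.** Section 2.3 has HBsAg assayed six-monthly. The control and interferon tables in section 5.3 mark it at weeks 0, 4, 24, 52, 104 and 156, so yearly after week 52. The two do not agree.
- **Confirmation.** Section 2.3 requires a second negative test at least one month after the first. It does not say which of the two dates is the date of loss.
- **End of follow-up.** Section 3.2 says "Patients will be followed for 3 years after randomisation". The last visit is at week 156, and the tolerance table in section 5.3 allows +/- 10 days around it in both arms.

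**The concern.** Kaplan-Meier assumes that a patient censored on a given day has the same later risk as those still under observation. That fails at the final visit. A patient tested there either has the event or is censored on that same day, and the day is whichever one in the window the patient happened to attend. Early attenders who are still positive leave the risk set, and the events of later attenders are then divided by a shrinking number. All patients in the window are answering one question (had HBsAg gone by week 156?), but the estimator treats their answers as successive risks and compounds them.

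At stake is the planned picture of the main outcome over time. A curve ending well above the primary proportions would mislead readers about the loss rate in each arm and would enlarge the apparent absolute difference.

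**Working it through.** **Inputs from the protocol.** Section 8.1 assumes for control a "conservative assumption for the rate of HBsAg loss in this group at 15% at 2 years and 20% at 3 years", and for interferon that "the rate of HBsAg loss in this group will be 30% at 2 years and 40% at 3 years". Week 156 is day 156 x 7 = 1092, so its window runs from day 1082 to day 1102, which is 21 days.

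**The plan's own figure.** The protocol gives no Kaplan-Meier figure, so the planning rates are checked through the sample size. With a pooled two-sided test,

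n = [1.960 x sqrt(2 x 0.30 x 0.70) + 1.282 x sqrt(0.20 x 0.80 + 0.40 x 0.60)]^2 / 0.20^2 = 108.2, rounded up to 109.

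This agrees with section 8.1: "at the P < 0.05 threshold would require 109 subjects in each arm". The rates are used as stated.

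**Assumptions.** Last-visit dates are uniform over the 21 days, attendance is unrelated to outcome, and for six-monthly testing the loss at 2.5 years is halfway between the 2- and 3-year rates.

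**Formula.** Let p be the chance that a patient still positive at the previous test is negative at week 156. With k days of the window left, 1/k of those still at risk attend that day, so the curve is multiplied by (1 - p/k). Over the whole window,

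S(end) = S(previous test) x product of (1 - p/k) for k = 21, 20, ..., 1.

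The correct factor is (1 - p), applied once. Because 1 + 1/2 + ... + 1/21 = 3.65, the last interval's loss is counted about 3.65 times on the cumulative-hazard scale.

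| Testing | Arm | p | Day 1092 | Day 1095 | End (day 1102) | True |
|---|---|---|---|---|---|---|
| Yearly | Control | 0.05/0.85 = 0.059 | 18.5% | 20.1% | 31.6% | 20% |
| Yearly | Interferon | 0.10/0.70 = 0.143 | 36.8% | 39.8% | 59.1% | 40% |
| Six-monthly | Control | 0.025/0.825 = 0.030 | 19.3% | 20.1% | 26.2% | 20% |
| Six-monthly | Interferon | 0.05/0.65 = 0.077 | 38.5% | 40.1% | 51.1% | 40% |

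The difference at the end of the curve is 59.1 - 31.6 = 27.5 points with yearly tests and 51.1 - 26.2 = 24.9 points with six-monthly tests, against a true 20.

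**Simulation check.** With 120 per arm, yearly tests and uniform dates, the mean end of the curve is 31-32% vs 59-60%. Results are much the same with 109 per arm or with 10% dropout. With bell-shaped dates (SD 4 days, assumed) the curve reads about 22% vs 44% at day 1095 and ends at about 35% vs 63%. With every result placed at its scheduled week it gives 20% vs 40%.

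**Date of loss.** Suppose loss is dated at the confirmatory test, taken here as 30 days later. The earliest such date for a patient first negative at week 156 is day 1082 + 30 = 1112, after the last censoring on day 1102. Only patients with events then remain at risk, and the curve falls to 100% loss. With yearly tests about 0.05 x 120 = 6 control and 0.10 x 120 = 12 interferon patients are in that position. The chance that control has none is 0.95^120 = 0.2%.

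**Cox model.** The planning rates imply a hazard ratio of ln(0.60)/ln(0.80) = 2.29. Simulation gave 2.26 with actual dates and 2.28 with scheduled weeks.

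**The case against.** The best counter-argument is that the protocol never says actual dates will be used. Scheduled weeks remove the problem, and event dates, censoring dates and the cut of the axis commonly belong in the analysis plan, to which section 8.2 defers. That stands in part: the distortion is conditional, and the missing date rule is not in itself a fault. But the protocol does name the estimator. Actual dates are its usual input, and it does not suit the visit schedule in the same document.

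Four stronger readings are tempting, and the documents do not support them.

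- **That the curve shows 31% vs 59% at 3 years.** It does not. Those are the values at day 1102. At day 1095, with uniform dates, it reads about 20% vs 40%, because patients not yet seen offset the inflation. That balance depends on the spread of dates, as the bell-shaped case shows.
- **That the 1- and 2-year secondary outcomes are biased.** Section 8.2(ii) defines them as the primary outcome at earlier times, and the primary outcome is a proportion. Nothing says that they are read off the curve.
- **That the Cox model must be replaced.** The hazard ratio barely moves.
- **That the primary result or the sample size is at risk.** Both rest on proportions and do not use the curve.

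It is also fair to object that the size depends on the testing interval, on which sections 2.3 and 5.3 disagree. Both cases are therefore given. The excess is smaller with six-monthly tests but does not vanish.

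**Conclusion.** The concern holds for the tail of a secondary display. If actual visit dates are used and the curve is drawn to the last visit, its final days overstate loss: about 31% vs 59% with yearly tests or 26% vs 51% with six-monthly tests, against 20% vs 40%. The absolute difference grows from 20 to about 25-28 points. These sizes rest on the section 8.1 rates and on assumed uniform visit dates. Dating loss at the confirmatory test, which section 2.3 leaves open, would take the curve to about 100% loss in any arm with a patient first negative at the last visit. The change is worth making because the curve will be read beside the primary proportions.

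**What to change.** In section 8.2(ii), or in the analysis plan, state that each HBsAg result is assigned to its scheduled week, that persistence is shown as a life-table estimate at those weeks, and that loss is dated at the first negative test that is later confirmed. An interval-censored (Turnbull) estimate between the last positive and the first confirmed negative test would serve equally well. The list of weeks depends on the testing interval, so sections 2.3 and 5.3 should be reconciled at the same time. The Cox model can stay.

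The cost is a sentence or two and a different procedure call, with no new data. The small downside is a step curve with few time points.

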2.5 Development of predictive biomarkers

Baseline and early dynamic changes in qHBsAg, ELISPOT and NK cell parameters will be used alongside clinical and laboratory analyses to construct prognostic models for the prediction of HBsAg loss.

[figure not shown]

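### The predictor model applies one significance screen to 12 candidates, two of which exist in only about 20 patients, and uses ALT and viral load peaks with no time window

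*Protocol*

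**What the plan says.** Section 8.2(iii) of the protocol sets up a two-stage analysis. A separate logistic model is fitted for each of 12 variables. The first seven are gender, age, duration of antiviral therapy, viral genotype, pre-treatment viral load, HBsAg titre and centre. The other five are "peak ALT value post withdrawal, peak viral load post withdrawal, hepatic cccDNA, number of infected hepatocytes and ELISPOT counts". The second stage is one multivariable model that "will include the variables that were statistically significant in the univariate analysis plus a variable for treatment group". No p-value threshold is given for the screen, and no window for the peaks.

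Section 5.1 says where the tissue variables come from: "Patients who consent to liver biopsy (estimated to be around 20 in number". Section 1.2.1 gives the same subset size but also allows fine needle aspirates. The infected-cell count needs biopsy immunohistochemistry, so it may be known in fewer than 20.

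Section 2.5 describes the prognostic models as follows: "Baseline and early dynamic changes in qHBsAg, ELISPOT and NK cell parameters will be used", alongside other clinical and laboratory data.

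Section 8.2(ii) leaves sensitivity analyses for missing data to the statistical analysis plan.

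**The concern.** Three features of the rule cause difficulty.

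- **Tissue variables share the entry rule of full-sample variables.** If one is selected, it joins predictors known in up to 240 patients. A standard logistic fit drops every patient without a biopsy, so the model loses most of its data because of which variable happened to be significant.
- **The peaks are unbounded.** ALT and HBV DNA are measured at every visit to week 156, so a peak may come after the HBsAg loss that it is meant to predict. Section 5 expects up to 45% of patients to need retreatment. ALT is itself one of the triggers in Section 6.5(i), so retreatment cuts peaks short. The number of measurements also varies: the schedules have 13 control visits and 16 interferon visits, and flares bring extra ones.
- **Univariate significance alone decides entry.** Section 5.2 calls HBsAg titre the strongest predictor of outcome in interferon-based treatment, yet it stays in the model only if it is significant in this sample.

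At stake is secondary objective 4, which is to find biomarkers for a group of patients in whom HBsAg loss is feasible.

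**Working it through.** **Inputs.** All are from the protocol: 3-year loss of 20% in the control arm and 40% in the interferon arm, 109 evaluable and 120 recruited per arm (Section 8.1), and about 20 patients with tissue (Sections 1.2.1 and 5.1).

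**1. The plan's own figure.** Section 8.1 sets the target: "A trial with 90% power to detect a difference in HBsAg loss between these groups (40% vs 20%) at the P < 0.05 threshold". The stated requirement is 109 per arm. With a two-sided 0.05 test (sidedness is not stated) and pooled variance:

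n = [1.96 × √(2 × 0.30 × 0.70) + 1.2816 × √(0.20 × 0.80 + 0.40 × 0.60)]² / 0.20² = (1.270 + 0.811)² / 0.04 ≈ 108.2, rounded up to 109. The figure reproduces, so its event rates are used below.

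**2. Events in the full data.** Recruited: 120 × 0.20 + 120 × 0.40 = 72. Evaluable: 218 × 0.30 ≈ 65.

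**3. Events if a tissue variable enters and the fit is complete-case.** 20 × 0.30 = 6, with 95% binomial limits 2 to 10. The count would be 4 if all 20 were control patients and 8 if all were interferon patients. For subsets of 15 to 25 the range is 3 (15 × 0.20) to 10 (25 × 0.40). Against 65 events, 6 is a loss of about 91%. One tissue variable plus treatment leaves 6 / 2 = 3 events per parameter; one more predictor leaves 2.

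**4. Precision for one standardised covariate.** SE of the log odds ratio ≈ 1/√(n × p × q).

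- n = 218: 1/√(218 × 0.21) = 0.148; detectable odds ratio at 80% power exp(2.8 × 0.148) ≈ 1.5.
- n = 20: 1/√(20 × 0.21) = 0.488; exp(2.8 × 0.488) ≈ 3.9.

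This is a large-sample, unadjusted formula. At 6 events it is only a rough guide.

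**5. How likely a tissue variable is to enter (0.05 assumed).** If neither matters and the two tests are independent at their nominal level: 1 − 0.95² = 9.75%. If one does matter, univariate logistic models were simulated with n = 20 and a 30% event rate:

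| True odds ratio per SD | Passes likelihood-ratio screen | Passes Wald screen |
|---|---|---|
| 1.5 | 14% | 4% |
| 2 | 30% | 12% |
| 3 | 52% | 23% |

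When a true odds ratio of 2 passes the likelihood-ratio screen, the median estimate is about 5.5.

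**6. The screen as a whole.** With 12 null, independent candidates at 0.05, at least one enters with probability 1 − 0.95¹² = 46%.

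**7. The peaks.** No arithmetic applies. Section 8.2(iii) fixes only the start of the window (withdrawal). The visit schedules supply ALT and HBV DNA to week 156, and Section 2.3 places HBsAg testing every 6 months. Nothing in the text requires a peak to come before HBsAg loss.

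**The case against.** The strongest reply is that this is an exploratory analysis with details still to come. The candidates are to be explored, odds ratios from every single-variable model are reported whatever the second stage does, and missing-data sensitivity methods are left to the analysis plan. Univariate screening is conventional in such work. The 46% needs independent nulls and a threshold that the protocol does not state, and several candidates are plainly related. Penalised regression does not directly give the odds ratios with 95% confidence intervals that the section promises.

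Most of that stands, and it limits the point. It does not remove it. The entry rule and the candidate list are fixed in the protocol, so the analysis plan would have to override them. Missing-data sensitivity analyses do not repair a predictor absent by design in 220 of 240 patients (about 92%).

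Three stronger readings are tempting but unsupported:

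- A reader might infer that the peaks are defined over the whole follow-up. The text allows that but does not say so.
- A reader might infer that the model will collapse, or cannot predict at all. The collapse needs a tissue variable to pass the screen and a complete-case fit. Without the tissue variables the model keeps about 65 to 72 events.
- A reader might see a flat contradiction with Section 2.5. There, the early changes refer to qHBsAg, ELISPOT and NK cell measures, and the accompanying clinical and laboratory data could include ALT and viral load with no limit on timing. The misfit is partial.

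**Conclusion.** The point holds in a limited form. As written, the selection rule can cut the multivariable model from about 65 to 72 events to about 6, through two variables known in about 20 patients. This rests on the protocol's assumed loss rates, a tissue subset that mirrors the 1:1 allocation, a 0.05 screen and complete-case fitting. It is a realistic possibility and not the expected result. Separately, the missing window lets in peaks that follow the outcome or are shaped by retreatment, so their odds ratios could not be read as prognostic.

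The case for replacing univariate screening altogether is weaker and partly a matter of preference. Leaving known predictors to chance significance is the part worth changing. The analysis serves secondary objective 4, and neither the primary comparison nor the sample size is affected.

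**What to change.** Amend Section 8.2(iii), or override it explicitly in the analysis plan, in three respects.

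1. Keep hepatic cccDNA and the number of infected hepatocytes out of the main multivariable model. Report them separately and descriptively in the tissue subset, with the number of patients who have each measurement.
2. Define peak ALT and peak viral load up to a pre-specified landmark, and model later HBsAg loss in patients still HBsAg-positive at that time. The team should choose the landmark, at a visit where HBsAg is assayed, and align the wording with Section 2.5.
3. Force pre-specified known predictors, at least HBsAg titre and treatment, into the model and do not rely on univariate significance alone. At an assumed 10 events per parameter, 65 to 72 events support about 6 to 7 parameters including treatment. Penalisation with bootstrap validation is an option.

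The cost is some wording and a little more programming, with no new data or patients. The real downside is that early HBsAg losers drop out of the landmark model. In the published withdrawal study cited in Section 8.1, loss was 10% at 1 year and 24% at 3 years, so a one-year landmark would set aside about 10/24 = 42% of the 3-year losses. An earlier landmark loses fewer, and a model with baseline predictors only can still use all patients.
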